4.0 Number of Participants

4.1

This study will enroll 1,500 participants at UW-Madison. There will also be a pilot of up to 15 participants. We will recruit approximately 250 healthy control participants who will complete baseline measures only.

4.2

The expectation is that we will have 20-50% attrition resulting in roughly 750-1200 participants completing the study.

4.3

Participants will be considered enrolled after randomization. Participants who leave the study early will not be replaced. Healthy control participants will only complete baseline measures.

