11.0 Study Intervention

11.1

The study intervention will be the Healthy Minds Program (HMP), a 4-week mobile health meditation training augmented with depression-specific content. The HMP was developed by our affiliated non-profit organization, Healthy Minds Innovations, Inc (HMI). The HMP is designed to promote and protect psychological well-being through sustainable skills training, with instruction administered through a curriculum of high-quality guided practices. The HMP is based on research on eudaimonic well-being (e.g., environmental mastery, purpose) and brain-based skills that underlie these qualities (e.g., regulation of attention, mental flexibility). The HMP has >100 guided audio practices that address 4 constituents of well-being: awareness, connection, insight, and purpose. The intervention and active control groups will download and use a study specific version of the HMP immediately after randomization. The intervention group will have access to and instructed to listen to both the lessons and meditations (guided practices). The active control group

PROTOCOL TITLE: Behavior, Biology, and Well-Being (BeWell) Study

will have access to and instructed to listen to the lessons only (meditation practices are not included). The intervention and active control groups will use the HMP for four weeks. The active control group and the usual care group will be given the opportunity to download and use the full HMP after they finish their 3-month follow-up assessment.

The following usage data is recorded: date, time, duration, device type, lesson or practice, week, foundation (awareness, connection, insight, or purpose), and name of lesson or practice.

Participants listen to lessons and/or practices and occasionally answer pre and post questions using their smartphones.

This study requested a non-significant risk (NSR) determination for the use of the HMP. Use of the HMP may mitigate symptoms of depression, anxiety and/or stress but has not shown to pose a risk to health or safety. Below is a copy of the NSR letter.

Request for a Non-Significant Risk Determination from the IRB for an Investigational Device

UW-Madison Health Sciences IRB:

Please accept this letter as a request for non-significant risk (NSR) determination for the investigational device evaluation described in the IRB submission titled “BeWell Study”.

The FDA defines significant risk devices as follows (21 C.F.R. § 812.3(m)):

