5. Weeks 1 to 3 Assessments (Timepoints 2, 3, 4). Participants will complete a small subset of the surveys in REDCap as well as the video task at the end of weeks 1, 2, and 3. It will take

PROTOCOL TITLE: Behavior, Biology, and Well-Being (BeWell) Study

approximately 30 minutes to complete these measures. Participants will be given one week to complete each weekly assessment.

6. Week 4/Post-Intervention Assessment (Timepoint 5). Participants will complete the same surveys and games (behavioral task and video task) in REDCap as was done for the pre-intervention assessment; the invite for these measures will be sent at the end of week 4. It will take approximately 60-90 minutes to complete these measures. Participants will be given 2 weeks to complete this assessment. Participants in the intervention or active control groups will have the option to continue using the HMP after this timepoint. We will continue to monitor app data throughout the study to learn more about its long-term impact on well-being.
7. 3-Month Follow-Up Assessment (Timepoint 6). Participants will complete the same surveys and games (behavioral task and video task) in REDCap as was done for the pre-intervention and post-intervention assessments; the invite for these measures will be sent 90 days after the date of the post-intervention invite. It will take approximately 60-90 minutes to complete these measures. Participants will be given 2 weeks to complete this assessment. Another microbiome kit and blood spot collection kit will be mailed to participants to collect samples; they will have 1 month to collect.

Healthy control participants will complete only #1 to #3.

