15.0 Withdrawal of Participants

15.1

We anticipate that we will withdraw a participant from the study: 1) if we determine that participation in the study is exposing the participant to an unacceptable level of risk, 2) to maintain data integrity (e.g., if a participant is not following study procedures or may be deliberately providing false information), or 3) if the study is stopped by the sponsor or researchers.

PROTOCOL TITLE: Behavior, Biology, and Well-Being (BeWell) Study

15.2

When withdrawing a participant, we will: 1) thank the participant for their participation, 2) explain the reason(s) for termination, 3) explain that the participant will be paid for the portion of the study that they completed (as described in the consent form), 4) ask the participant if they have any questions or comments about the study, and 5) inform the participant that the HMP app is available to use free of charge. We will change the participant status to withdrawn in REDCap; however, we will retain and use data collected prior to withdrawal.

15.3

When a participant chooses to withdraw from the research, we will: 1) thank the participant for their participation, 2) determine if the participant will be fully or partially withdrawing (if partial, determine which procedures the participant will be completing), 3) explain that the participant will be paid for the portion of the study that they completed (as described in the consent form), 4) ask the participant their reason for withdrawing (if they choose to provide it), 5) ask the participant if they have any questions or comments about the study, and 6) inform the participant that the HMP app is available to use free of charge. We will remove the withdrawn participant from REDCap; however, we will retain and use data collected prior to withdrawal.

15. 4

Participants who withdraw or do not complete baseline may be asked why they did not continue with participation.

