20.0 Study Analysis

20.1

HMP will show greater improvements in (a) depression, (b) psychological distress, (c) well-being, (d) and performance on the pattern separation task vs. both the active control (HMP psychoeducation) and usual care conditions.

20.2

We plan to enroll 1500 participants in this study, assigning two fifths to HMP, two fifths to the active control, and one fifth to a usual care. Anticipating 20% dropout, this sample will provide 80% power to detect small differences between HMP and the active control ($d = 0.20$) and 80% power to detect small-to-moderate differences between HMP and the usual care ($d = 0.28$).

PROTOCOL TITLE: Behavior, Biology, and Well-Being (BeWell) Study

We plan to recruit approximately 250 healthy controls at baseline. This will allow statistical power to detect small between-group differences on baseline measures.

20.3

Participants will be randomized into 3 different groups: two-fifths to intervention, two-fifths to active control and one-fifth to waitlist control. All study procedures will be the same across all groups except the use or non-use of HMP.

Healthy control participants will not be randomized.

20.4

Group differences for the intervention will utilize linear mixed effects models to account for non-independence and to maximize use of data with missing observations.

20.5

Given the low risk of the intervention, no interim efficacy or safety analyses are planned.

20.6

Linear mixed effects analyses account for missing data in a robust manner relative to, e.g., ANOVA. If differential attrition is observed (e.g., between HMP and usual care), we may conduct sensitivity analyses to evaluate the potential impact of data missing not at random.

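### The only check for data missing not at random is optional and waits for an undefined differential attrition, yet balanced dropout rates would not show that the HMP contrasts are unbiased

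*Combined protocol and SAP*

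**What the plan says.** Section 20.4 gives the primary analysis: "Group differences for the intervention will utilize linear mixed effects models to account for non-independence and to maximize use of data with missing observations". Section 20.6 calls this robust relative to ANOVA and does not state the missing-at-random assumption. On departures from that assumption it then adds: "If differential attrition is observed (e.g., between HMP and usual care), we may conduct sensitivity analyses to evaluate the potential impact". No rate, test, visit or outcome defines differential attrition; an example pair of arms is all that is given. No sensitivity method is named, and no other section provides for data missing not at random.

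On the amount of missing data, section 4.2 states: "The expectation is that we will have 20-50% attrition resulting in roughly 750-1200 participants completing the study". Section 4.3 counts enrolment from randomization without replacement, so this is post-randomization loss. Section 20.2 sizes the trial for 20% dropout, with 1,500 participants allocated 2:2:1 and target effects of d = 0.20 (HMP vs active control) and d = 0.28 (HMP vs usual care).

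**The concern.** A likelihood-based mixed model is a reasonable primary analysis, but it is unbiased only if, given the scores already seen, dropout does not depend on the unseen score. That cannot be tested from the observed data, and comparing dropout rates between arms does not test it. Two arms can lose the same proportion for different reasons.

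Under the current wording, a trial with balanced rates and heavy loss could be reported with no check at all. Even where rates differ, the check may be left out. In both cases the decision falls after arm-level attrition has been seen. What is at stake is how far a small effect on a self-reported primary endpoint can be trusted when up to half of the scores at the last visit may be missing.

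**Working it through.** **Plan's own figures.** Completers: 1,500 × 0.80 = 1,200 and 1,500 × 0.50 = 750, as section 4.2 says. Power: the documents state no alpha. At two-sided 0.05 with 20% dropout, Φ(0.20/√(2/480) − 1.96) = 87% and Φ(0.28/√(1/480 + 1/240) − 1.96) = 94%, against the stated 80% for each. The stated powers are conservative on that assumption. This is a separate matter and nothing below depends on it.

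**Bias with equal rates.** Let delta be the mean distance of an arm's dropouts' unseen PHQ-8 from its missing-at-random prediction, in SD units. The model sets delta to zero. With attrition p in both arms:

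bias = p × (delta_HMP − delta_comparator)

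It is zero if the deltas are equal and can have either sign if they differ.

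**Delta difference that equals the target (d/p).**

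| Contrast | p = 20% | 35% | 50% |
|---|---|---|---|
| Active control, d = 0.20 | 1.00 | 0.57 | 0.40 |
| Usual care, d = 0.28 | 1.40 | 0.80 | 0.56 |

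**Illustration.** The following are assumptions, not document figures. Missingness is logistic in the unseen score, with odds ratio 1.65 per SD in one arm and 1.3 in the other, and equal total attrition. Earlier PHQ-8 scores are seen for everyone. At post-intervention there are four earlier scores, all correlated 0.6, so R² = 4 × 0.36/(1 + 3 × 0.6) = 0.514. At 3 months there are five, correlated 0.6 with each other and 0.5 with follow-up, so R² = 5 × 0.25/(1 + 4 × 0.6) = 0.368. Numerical integration gives:

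| Visit | Bias at 20/35/50% (SD) | Implied delta difference (bias/p) |
|---|---|---|
| Post-intervention | 0.022/0.037/0.053 | about 0.11 |
| 3 months | 0.028/0.048/0.069 | about 0.14 |

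Swapping the arms reverses the sign. Equal odds ratios give 0.000.

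**Would that overturn a target-size result?** The threshold must come from the same model:

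SE² = (1/n1 + 1/n0) × [V + (1 − R²)/(1 − p)]

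V = R² without baseline adjustment, or R² minus the squared correlation with baseline when adjusted. The difference that removes significance is (d − 1.96 SE)/p. The ranges below run from unadjusted to adjusted.

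HMP vs active control (600 vs 600, d = 0.20):
- 50%, post-intervention: 1.96 SE = 0.138 to 0.120, threshold 0.12-0.16. Effect left: 0.20 − 0.053 = 0.147, still significant.
- 50%, 3 months: 1.96 SE = 0.145 to 0.133, threshold 0.11-0.13. Effect left: 0.20 − 0.069 = 0.131, significance just lost.
- 35%, both visits: threshold 0.20-0.26, so neither result is overturned.

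HMP vs usual care (600 vs 300, d = 0.28):
- 50%, 3 months: 1.96 SE = 0.177 to 0.163. Effect left: 0.28 − 0.069 = 0.211, still significant.

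**False positives.** With no true effect, Φ(b/SE − 1.96) + Φ(−b/SE − 1.96) at 3 months against active control gives about 7-8% at 20% attrition (b = 0.028, SE = 0.062 to 0.055) and 15-17% at 50% (b = 0.069, SE = 0.074 to 0.068). Equally informative dropout stays near 5%.

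**The case against.** Several points on the other side stand.

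- The mixed model uses weekly PHQ-8 scores, which carry much of the information about a later missing value. At 20% attrition a moderate asymmetry does little.
- Differential attrition could be read more widely, to cover who leaves and why; section 15.3 asks for reasons at voluntary withdrawal. But the plan does not say so, links reasons to no analysis, and would still commit to nothing.
- The 20-50% range concerns completing the study. It fits the 3-month visit best, and no per-visit rate is given. The long assessment before randomization and the $50 completion bonus make the upper end less likely, without removing it.
- Over a wide enough delta range, some value will always reverse a positive result. The range therefore needs a justification in advance.

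A reader might infer that the app-access rules show HMP dropouts to differ from comparator dropouts in a known direction. The documents do not support that. Section 11.1 says the active control and usual care groups "will be given the opportunity to download and use the full HMP after they finish their 3-month follow-up assessment", which could affect who stays. But section 13.1 lets both app groups go on using their versions after week 4, and the instruction in section 15 to "inform the participant that the HMP app is available to use free of charge" applies at withdrawal in every arm. Unequal deltas are possible; their size and direction are unknown.

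**Conclusion.** The concern holds as a weakness of the stated rule. The only check for data missing not at random is optional, and on the natural reading its trigger looks at the wrong quantity. The formula for equal attrition needs no assumption about mechanism, and the cancelling differences follow from the plan's own attrition range and target effects.

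The consequence is moderate. The illustrative bias, 0.02 to 0.07 SD, rests on assumed odds ratios and correlations. It removes significance from a target-size result only marginally, near 50% attrition, at 3 months, against active control.

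A reader might go further and conclude that the post-intervention result, the usual-care contrast, or the whole upper half of the attrition range is at risk of reversal. Under this asymmetry the matched thresholds do not bear that out. Nor does anything here show that the contrasts will be biased, or that the mixed model is the wrong primary analysis.

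**What to change.** Replace the conditional sentence in section 20.6 with wording such as:

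*Whatever the observed balance of attrition, the PHQ-8 contrasts of HMP with active control and with usual care at post-intervention and 3-month follow-up will be re-analysed by multiple imputation with delta adjustments allowed to differ by arm, over a range justified in advance; the delta differences at which the conclusion changes will be reported.*

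The deltas must be free to differ by arm, because a common delta cancels when attrition is equal. The sponsor should justify the range on clinical or prior-data grounds; the thresholds above help in reading the result and do not justify a range. If differential attrition is kept for descriptive reporting, define it.

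Cost: one sentence of plan text, a few days of analysis and no new data. The downside is that a conclusion may have to be reported as less robust.

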21.0 Potential Benefits to Participants

21.1

Participants may benefit from using the HMP, which is designed to introduce meditation practice as a way of reducing stress and developing greater balance, ease, and fuller participation in life. This meditation training teaches well-being skills which can be used in everyday life to cope with the challenges of stress, pain, illness, and everyday demands. Usual care and active control participants can use the full version of HMP after completion of the study at no cost.

21.2

There are no direct benefits for participants.

22.0 Risks to Participants

22.1

Breaches of Confidentiality

Risk of confidentiality breach is minimized due to data storage procedures employed (i.e., data coding, secure storage, trained personnel). We obtained a certificate of confidentiality due to the nature of some of the data collected.

PROTOCOL TITLE: Behavior, Biology, and Well-Being (BeWell) Study

Because there is potential for the study to capture information that could lead to reporting intention to harm self, participants will be informed in the consent form of this limit to confidentiality before they agree to participate. The researchers would report to the study psychologist on call and/or emergency services, as dictated by the specific circumstances. We have well-established protocols for handling suicidality and threat of harm to self.

Emotional Upset

Emotional upset due to study participation is a potential but unlikely risk of study activities. In our experience, it is rare for a participant to find self-report questionnaires to be extremely upsetting. Participants will be informed that they are free to decline answering any question for any reason.

The interview consists of the Depressive Disorders and related modules of the Structured Clinical Interview for DSM-5 Research Version (SCID-5-RV). If a participant reveals suicidal ideation, self-harm or intent to harm others, the clinical research personnel will assess intent. In the circumstance that an individual indicates that self-harm or harm to others is imminent, 988 and/or 911 (or local authorities in the county/city where the participant lives) will be called. The clinical research interviewers will consult with qualified study personnel with mental health expertise as needed. The clinicians may contact the participant by phone to further assess the level of risk and provide additional referrals as needed. All interactions regarding suicide risk and referral will be carefully documented and closely tracked by the study clinician. A formal incident report will be filed with the IRB in cases in which the clinician notifies authorities. All eligible participants will be provided with the "Therapeutic Resources" list regardless of their responses. All individuals who are excluded from the study during the screening process or interview will be given the "Therapeutic Resources - Exclusion" list which has links to the Virtual Hope Box, suicide hotline, and mental health website.

There are no physical risks involved in collecting the microbiome sample. It will be integrated as part of their regular routine, with the only difference being that this bowel movement will be collected in a plastic container. They may experience some slight psychological discomfort or embarrassment about collecting this sample.

Physical Risks

Some tenderness may be experienced at the site of the finger prick for the blood spot collection. Occasional bruising at the site can occur and is not permanent. In very rare cases, infection at the site can occur. Single-use lancets will minimize the risk of infection.

22.2

N/A

22.3

N/A

22.4

N/A

PROTOCOL TITLE: Behavior, Biology, and Well-Being (BeWell) Study

22.5

N/A

22.6

The exclusion criteria limits the number of people who are at high risk for self-harm from the study. Conducting the interview only after all of the pre-intervention surveys are completed, decreases the number of potential participants who have sensitive information collected as part of the screening process.

23.0 Provisions to Monitor the Data to Ensure the Safety of Participants

23.1

Adverse events will be tracked (including details of the incident, actions taken, and follow-up steps) by study staff and reported to the PI. The PI will be responsible for the monitoring and reporting of adverse events as necessary to the UW IRB.

Other notable incidents that occur during recruitment, consent, study assessments, but are determined to be unexpected and related to the study procedures, will be reported in a detailed log on an annual basis (at the time of continuing review). The PI will be responsible for informing the IRB immediately of any life-threatening incidents as well as take appropriate action to stop the study, release a participant from the study, or modify procedures to reduce and/or eliminate the occurrence of the risks mentioned above.

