- ““(1) Is intended as an implant and presents a potential for serious risk to the health, safety, or welfare of a subject;
- (2) Is purported or represented to be for a use in supporting or sustaining human life and presents a potential for serious risk to the health, safety, or welfare of a subject;
- (3) Is for a use of substantial importance in diagnosing, curing, mitigating, or treating disease, or otherwise preventing impairment of human health and presents a potential for serious risk to the health, safety, or welfare of a subject; or
- (4) Otherwise presents a potential for serious risk to the health, safety, or welfare of a subject””

The Healthy Minds Program (HMP) in this study is a smartphone app that includes both didactic content and guided meditation practices. The device will be used to aid development of well-being by training skills that are based on scientific studies (the didactic content). It also includes guided meditation practices found in widely available evidence-based treatments such as mindfulness-based stress reduction, mindfulness-based cognitive therapy, cognitive behavioral therapy, acceptance and commitment therapy, and other widely used smartphone meditation apps such as Headspace and Calm.

The use of the device in this study does not meet the definition of a significant risk device as it is not an implant, is not used to sustain human life and poses no serious risk to health, safety or

PROTOCOL TITLE: Behavior, Biology, and Well-Being (BeWell) Study

welfare of a subject. The device may mitigate symptoms of depression, anxiety and stress, but has not shown to pose a serious risk to health, safety, or welfare.

Summary of prior uses: HMP has been tested by our group in two randomized controlled trials (ns = 343, 662; Goldberg et al., 2020; Hirshberg et al., 2021). In both trials, HMP was shown to produce larger reductions in psychological distress (composite of depression, anxiety, and stress) relative to a waitlist control condition. Participants in both studies were drawn from the general population, although ~75% in each sample reported elevated depression and/or anxiety symptoms at baseline. Effects were similar when restricted to those in the clinical range at baseline. No serious adverse effects were reported in either study. In support of HMP's safety, HMP was shown to produce lower rates of clinically significant increases in symptoms relative to a waitlist condition.

References:

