25.0 Resources Available

Will the research be conducted outside School of Medicine and Public Health or UW Hospitals and Clinics (e.g. the researcher does not have an SMPH research feasibility attestation for this study)?	 YES (complete 25.1)  NO (remove text below, but retain this section)
---	---

25.1

The Center for Healthy Minds has extensive experience running large-scale, longitudinal studies. As most studies have moved to remote data collection in the past year (IRB

PROTOCOL TITLE: Behavior, Biology, and Well-Being (BeWell) Study

protocols: 2020-0533, 2020-1454, and 2019-0893), we have been successful at recruiting a large number of participants with high retention rates.

This study will be conducted over a three-year period, with all study collection being done remotely. Each participant will be involved with the study for approximately 4 months.

Study staff will meet on a regular basis to discuss study design, implementation, processing and analyses. Any task assignments and study updates will be discussed at these meetings. The study also uses the Basecamp platform (a project organization platform) to discuss any questions, updates, and changes to the study.

All participants will be informed to contact their healthcare provider if any concerns arise when answering survey questions. A therapeutic resource list will be provided to all participants via REDCap.

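### Section 23.1 sends residual incidents judged unexpected and study-related to an annual log, so those outside the other reporting routes can reach the IRB up to about 12 months late

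*Combined protocol and SAP*

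**What the plan says.** Section 23.1 sets out three routes to the IRB, and two other sections add a fourth.

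- **Adverse events.** Staff track them and report them to the principal investigator. Then: "The PI will be responsible for the monitoring and reporting of adverse events as necessary to the UW IRB". No criterion or time limit is attached.
- **Residual incidents.** The next paragraph turns to other notable incidents in recruitment, consent or study assessments. Those that arise there "but are determined to be unexpected and related to the study procedures, will be reported in a detailed log on an annual basis", at continuing review.
- **Life-threatening incidents.** "The PI will be responsible for informing the IRB immediately of any life-threatening incidents". The same sentence makes the investigator responsible for stopping the study, releasing a participant or changing procedures where needed.
- **Authorities notified.** Sections 13.3 and 22.1 require a formal incident report to the IRB when the clinician contacts authorities about self-harm or harm to others. No time limit is given.

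On the wider safety plan, Section 3.4 lists no safety endpoints, and Section 20.5 says that "no interim efficacy or safety analyses are planned". The non-significant-risk letter in Section 11.1 relies on two earlier trials of the app: "No serious adverse effects were reported in either study". On duration, Section 25.1 says: "Each participant will be involved with the study for approximately 4 months".

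**The concern.** An incident that is both unforeseen and caused by the study is evidence of a risk that the approved protocol and consent did not describe. That makes it a natural candidate for early outside review. This is a reviewer's judgement; the documents do not say it. Within its residual class, Section 23.1 does the opposite: meeting both conditions is what places an incident in the annual log, and once a year is the slowest timetable stated anywhere in that section.

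With no safety endpoints and no interim safety analysis, incident reporting to the IRB is the only outside check on safety that the documents describe while the trial runs. If an incident of this kind waits for continuing review, the IRB cannot ask for a change in procedures or consent in the meantime, and recruitment, which Section 7.4 describes as continuous, goes on.

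**Working it through.** The point rests on the text and not on a power or sample-size figure, so there is no planned figure to reproduce. The check has two parts.

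**1. Which incidents have no faster route?** Take an incident that staff judge unexpected and related, and pass it through the routes in turn.

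- Life-threatening? It goes to the IRB immediately (23.1).
- Handled as an adverse event? It goes to the investigator, and to the IRB as judged necessary (23.1). There is no deadline, but no tie to the annual log either.
- Authorities notified? A formal incident report is filed (13.3, 22.1).
- None of these? It goes in the annual log (23.1). No other section gives a faster route.

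The last class is not empty. Section 16.6 treats the face and voice recordings as identifiable and allows them to be shared, with the decryption key, under a data use agreement. Section 16.2 says that the recordings come through a separate app. A release of video by some unforeseen means is not life-threatening, is not naturally an adverse event and involves no call to authorities. If it is judged unexpected and related, it is logged for continuing review.

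**2. How long is the delay?**

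- Inputs: reporting interval of one year (23.1); participation of about 4 months (12.1, 25.1); 1,500 randomized participants (4.1); recruitment throughout a 3-year study (7.4).
- Longest delay: an incident just after one continuing review waits about 12 months for the next.
- Average delay: 12 / 2 = about 6 months, assuming that incidents fall evenly over the year.
- Against participation: 12 − 4 = 8. A participant who starts on the day of such an incident could finish about 8 months before the IRB sees the log.
- Enrolment during the delay, assuming even accrual: 1,500 / 3 = 500 randomized per year, so 500 × 6/12 = 250 in an average delay.
- If one year takes between 20% and 50% of the total, that year has 0.20 × 1,500 = 300 to 0.50 × 1,500 = 750 randomized. A 6-month delay then covers 150 to 375.

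The enrolment figures are illustrations under assumed accrual. They count people who join during a delay, not people exposed to a hazard, and the documents give no incident rate from which to go further.

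**The case against.** The strongest reply is that the class is small. A reader who sees only the log sentence might infer that every unexpected and related incident waits a year. The documents do not support that: the sentence concerns what is left after adverse events, and the gravest incidents have their own routes. This objection stands, and it limits the point to the residual class.

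Four further objections:

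- **Examples.** Marked distress caused by a task might seem to belong in the log, but it is naturally an adverse event. Section 22.1 names confidentiality breach as a foreseen risk, so an ordinary breach may not count as unexpected. Both points stand, which is why the example here is an unforeseen type of release. The second also exposes a loose end: a breach judged expected has no clear route in 23.1.
- **App use.** The log sentence lists recruitment, consent and assessments, so a reader might infer that harms from the app go unreported. They do not: the adverse-event sentence has no phase limit, adverse events are assessed at visits 5 and 6 (13.2), and the app groups complete an adverse-effects scale after the intervention (13.3). Only the wording of the log sentence is incomplete.
- **Action without the IRB.** The investigator can stop the study or change procedures (23.1), and participants at unacceptable risk can be withdrawn (15.1). This stands as mitigation. It does not replace review by someone outside the study team.
- **Drafting slip or outside policy.** The word *but* sits oddly in the log sentence and may be a slip about which incidents belong there. IRB policy may also already demand faster reporting. Neither can be settled from the documents. Section 23.1 cites no such policy and states an annual interval, so the text needs correction either way.

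**Conclusion.** The point holds for a defined class: incidents judged unexpected and related to study procedures that are not life-threatening, not handled as adverse events and not notified to authorities. For these, the stated rule allows a delay of up to about 12 months, or about 6 months on average if incidents fall evenly, against about 4 months of participation. The adverse-event route is a lesser weakness: it has no stated timing, but it is not annual.

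A reader might also infer that hundreds of participants would be exposed to an unaddressed hazard. The documents do not support this. The enrolment figures depend on assumed accrual, no incident rate is given, and the investigator may act before the log is read.

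The conclusion assumes that the sentence is applied as written and that no outside IRB policy overrides it. The study is described as minimal risk (9.2), which makes such incidents less likely but does not justify the slowest route for them. The change is worth making because it is small and bears on participant safety. It does not affect the validity of the trial's results.

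**What to change.** Amend Section 23.1 as follows.

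1. Report any incident judged unexpected and related to the study promptly to the IRB, whether or not it is life-threatening, within a stated time limit agreed with the IRB. Immediate notice of life-threatening incidents stays as it is.
2. Keep the annual log for incidents that are expected or unrelated. This also gives a route to foreseen incidents that now have none.
3. Word the sentence to cover all study phases, including app use.
4. While the section is open, state when an adverse event must go to the IRB and how soon.

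The cost is a few sentences in the protocol and a few extra IRB reports. Data collection, analysis and sample size are unaffected.
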